#### 4.6.2 Protocol Deviations

Major protocol deviations are defined as those deviations from the protocol likely to have an impact on the perceived efficacy and/or safety of study treatments. The impact of major protocol deviations on the efficacy and/or safety results will be investigated by assessing the robustness of the study results and conclusions to the choice of analysis set, both including and excluding data potentially affected by major protocol deviations, if applicable.

Major protocol deviations and any action to be taken regarding the exclusion of subjects or affected data from specific analyses are defined in the Protocol Deviation Specification.

The following summaries will be presented:

- The number and percentage of subjects with a major protocol deviation by treatment group and overall and by type of deviation (Analysis set: mITT).
- The number and percentage of subjects with any COVID-19 related protocol deviation (either major or minor) by treatment group and overall and by type of deviation (Analysis set: mITT).
- A by-subject listing of major protocol deviations and COVID-19 related protocol deviations will be provided.

#### 4.7 Demographic and Other Baseline Characteristics

Demographic variables and other baseline characteristics will be summarized for each treatment arm based on all randomized subjects (mITT analysis set) and for the two treatment arms combined (total). The variables to be summarized will include (but will not be limited to):

- Age (continuous variable)
- Age group (< 65 vs.  $\geq$  65)
- Gender
- Race
- Ethnicity
- Body mass index (BMI), calculated as weight (kg)/(height [m])

- Stratification factors used in the randomization
  - Number of prior therapies (1 or  $>1$ )
  - Bulky disease status (longest diameter of baseline lesion  $< 5$  cm or  $\geq 5$  cm)
  - Time since last recurrence ( $\geq 24$  months or  $< 24$  months)
- ECOG performance status
- Number of prior therapies ( $< 3$  or  $\geq 3$ )
- Months from initial diagnosis to randomization (calculated as date of randomization – date of initial diagnosis + 1)/(365.5/12)
- Months from last recurrence (calculated as date of randomization – date last recurrence + 1)/(365.5/12)
- iNHL subtype: FL, SLL or MZL; for MZL subjects type of MZL will also be categorized: splenic, nodal, or extranodal
- Specific prior therapies received (i.e., prior surgery, radiotherapy, chemotherapy, and other systemic anticancer therapies, including timeframe in which they were received, where applicable)

Age will be calculated as the number of complete years between a subject's birth year and the date of informed consent.

#### 4.8 Prior and Concomitant Medication

The World Health Organization - Drug Dictionary (WHODrug) will be used for concomitant and prior medications coding. Medications will be considered as prior if they stopped before the date of first dose of study drug. Medications will be considered concomitant if they were taken at any time between the first dose of study drug and 30 days after the last dose of study drug, inclusive. If the start date or end date of a medication is completely or partially missing refer to [Section 4.3.1.3](#) for the algorithm to determine whether a medication is concomitant.

Prior medications and concomitant medications will be summarized separately. Both summaries will be based on the AT analysis set. Medications will be summarized by Anatomical Therapeutic Chemical (ATC) classification level 2, and preferred drug name for each treatment arm. The summary will be sorted alphabetically by ATC level 2 and then by decreasing frequency by preferred drug name. A subject taking the same drug multiple times will be counted only once.

A listing will be provided for all non-study medications taken on the study. An identifier will be provided to show if a medication is prior or concomitant. Medications that started more than 30 days after the last dose of study drug will be identified as post-treatment. Additional groupings of medications will be defined to identify medications administered to treat AEs specific to the duvelisib risk profile.

## 4.9 Medical History

Medical history will be summarized and based on the AT analysis set. Medical history will be summarized by system organ class (SOC) and preferred term (PT) using the number and percentage of subjects who had at least one occurrence of a SOC or PT. The summary will be sorted alphabetically by SOC and by decreasing frequency of PT within an SOC.

## 4.10 Efficacy Evaluation

### 4.10.1 Analysis and Data Conventions

This study will test the null hypothesis that the ORR for each arm is  $\leq 30\%$  against the alternative that ORR is  $\geq 55\%$ . Each treatment arm will be evaluated separately; no formal comparisons between treatment arms are planned. The ORR (proportion of subjects achieving a CR or PR) will be estimated, along with the 2-sided 95% exact CI.

#### 4.10.1.1 Multi-center Studies

Statistical analyses will not control for sites; however, subgroup analyses for region (North America or Rest of World) will be performed for the primary endpoint, as well as the secondary endpoint of ORR per Lugano criteria.

#### 4.10.1.2 Adjustments for Covariates

Adjustments for covariates will not be performed for this study

#### 4.10.1.3 Handling of Dropouts or Missing Data

In general, values for missing data will not be imputed unless methods for handling missing data are specified. For analyses of ORR, subjects who do not exhibit a response will be classified as non-responders. For analyses of time to event endpoints, including DOR, PFS, OS, and TTF, subjects for whom the event is not observed will be censored as described in [Section 4.10.3](#).

#### 4.10.1.4 Multiple Comparisons/Multiplicity

Each treatment arm will be analyzed separately with no adjustment for multiplicity.

#### 4.10.1.5 Interim Analyses

No formal interim analysis is planned. Study data for each arm will be evaluated at the end of Stage 1 to determine whether a study arm should be terminated or continued to Stage 2. Please see additional details of the 2-stage design in [Section 4.13](#) below.

#### 4.10.1.6 Examination of Subgroups

The uniformity of the treatment effect for ORR (using both revised IWG and Lugano criteria) will be examined for the following subgroups:

1. Stratification factors
  - o Number of prior therapies (1 vs. > 1)
  - o Bulky disease status (longest diameter of baseline lesion < 5 cm vs.  $\geq$  5 cm)
  - o Time since last recurrence ( $\geq$  24 months vs. < 24 months)
2. Baseline ECOG score (0 vs.  $\geq$  1)
3. Region of world (North America vs. Rest of World)
4. Additional characterization of number of prior systemic regimens (1, 2, or  $\geq$  3)
5. iNHL subtype (FL, MZL, SLL)
6. Prior treatment with rituximab (yes vs. no)
7. Prior treatment with bendamustine (yes vs. no)
8. Age (< 60 years,  $\geq$  60 years)
9. Sex (male, female)
10. Ethnic origin (Caucasian, non-Caucasian)

Forest plots will be used to plot response rate by study Arm for each subgroup.

#### 4.10.2 Primary Efficacy Variable – ORR

The ORR (proportion of subjects achieving a CR or PR using the number of subjects in the mITT analysis set as the denominator) will be estimated, along with the 2-sided 95% exact CI using the Clopper-Pearson exact method for binomial proportions. Responses for the primary ORR analysis will be assessed using the 2007 revised IWG criteria (Cheson 2007). Missing data will be imputed by assuming that any subjects not exhibiting a response (CR or PR) are non-responders. Responses occurring after the start of subsequent anticancer therapy will not be included in the numerator.

The primary analysis of ORR will be performed 12 months after the last subject is randomized, using the time windows specified in [Section 4.2](#) as applicable.

A by-subject listing of the primary efficacy data will be provided.

#### 4.10.3 Secondary Efficacy Variables

The secondary efficacy analyses will be conducted on the mITT analysis set.

- ORR according to 2014 Lugano criteria (Cheson 2014) will be analyzed in the same fashion as the primary endpoint

*Note: with the exception of TTF, all additional secondary response endpoints (described below) as well as PFS will be assessed separately using 2007 revised IWG criteria (Cheson 2007) and 2014 Lugano criteria (Cheson 2014)*

- ORR, at 6, 12, 18, and 24 months after first dose of study intervention, defined as the proportion of subjects achieving CR or PR at each of these time points.
- PFS will be assessed using KM methods from time of first dose of study intervention to PD or death. Median PFS will be estimated, along with the 95% CI. The 6-month and 12-month PFS estimates will also be presented. See Table 1 for event and censoring definitions. Kaplan-Meier survival curves by arm will be produced.
- TTF will be calculated as the time from first dose of study intervention until discontinuation for any reason and will be summarized using KM methods. Median TTF will be estimated, along with the 95% CI. The 6-month and 12-month TTF estimates will also be presented. Subjects who are still on treatment at time of data cutoff will be censored at their last dose date. Kaplan-Meier survival curves by arm will be produced.
- DOR will be calculated for those subjects with a CR or PR from the time of first response to PD using KM methods. Median DOR will be estimated, along with the 95% CI. The 6-month and 12-month DOR estimates will also be presented. See Table 1 for event and censoring definitions. Kaplan-Meier survival curves by arm will be produced.
- OS will be assessed using KM methods from time of first dose of study intervention to death. Median OS will be estimated, along with the 95% CI. The 6-month and 12-month OS estimates will also be presented. Subjects without documented death will be censored at their last known alive date. Kaplan-Meier survival curves by arm will be produced.
- LNRR will be calculated as the proportion of subjects achieving  $\geq 50\%$  decrease in the sum of the product of the diameters of target lymph nodes. A 2-sided 95% exact CI for LNRR will also be estimated. A waterfall plot of minimum percent change in the sum of the product of the diameters by arm will be produced.
- TTFR will be calculated for those subjects with a CR or PR from the time of first dose of study intervention to time of first CR or PR. TTFR will be summarized descriptively (mean, SD, median, range). Kaplan-Meier survival curves by arm will be produced.

A by-subject listing of DOR, PFS and OS data will be provided.

**Table 1: Primary PFS Censoring/Event Rule**

Situation	Date of Event or Censoring	Outcome
No adequate baseline disease status assessment	Date of randomization + 1 day	Censored

No adequate post-baseline disease status assessment unless death occurs prior to first scheduled post-baseline assessment	Date of randomization + 1 day	Censored
No documented progression or death	Date of last adequate disease status assessment	Censored
Documented progression with $\leq 1$ missing scheduled disease status assessment before progression	Date of the earliest assessment that results in a finding of unequivocal progression	Event
Death before progression being documented with $\leq 1$ missing scheduled disease status assessment before death	Date of death	Event
Documented progression or death following a gap between adequate disease status assessments equivalent to 2 missed visits	Date of last adequate disease status assessment before the gap	Censored
New anticancer treatment or procedure started before documented progression	Date of last adequate disease status assessment prior to start of new anticancer therapy	Censored

Note: Disease status assessment includes radiologic documentation (CT, PET/CT, MRI scans) (chest, abdomen and pelvis, others as clinically indicated), bone marrow biopsy/aspirate (may not be required of all patients at all scheduled disease status assessments), and focused physical examination (disease related symptoms, liver and spleen assessment). An adequate baseline disease assessment is any assessment with measurable target lesions from scans. An adequate post-baseline disease status assessment is any disease status assessment for which a disease status of CR, PR, SD or PD is arrived per revised International Working Group (IWG) response criteria for malignant lymphoma.

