Clinical Chemistry, including Liver Function Tests	X	X	X	X		X	X		X	X		Liver function tests include LDH, serum ALT, serum AST, total and direct bilirubin, and ALP. Testing must be conducted, and results available, within 7 days prior to administration of first dose of duvelisib. Screening test results can be used for C1D1 if tests are performed within 7 days of C1D1.			
Immunoglobulin blood levels	X			X			X		X (even # cycles)			IgA, IgG, IgM			
Hematology	X	X	X	X	X	X	X		X	X		Hematology panel plus a 5-part differential. Testing must be conducted, and results available, within 7 days prior to administration of first dose of duvelisib. Screening test results can be used for C1D1 if tests are performed within 7 days of C1D1.			
Urinalysis	X	X		X			X		X	X		Qualitative analysis for protein performed at Screening, at C1D1, C2D1 and C6D1. If positive, quantitative analysis is needed if not previously noted as part of medical history. Testing must be conducted, and results available, within 7 days			

Activity	Screening D-30 to D-1	Cycle 1					Cycle 2		Cycle 3+	EoT ^a	Safety F/U ^b 30d (+7) postdose		Notes
		D1	D14 (-3)	D29 (+3)	D43 (±3)	D57 (±3)	D1 (±3)	D14 (-3)					
													prior to administration of first dose of duvelisib. Screening test results can be used for C1D1 if tests are performed within 7 days of C1D1.
ECOG Performance Status	X	X		X			X		X	X			If the ECOG Performance Status assessed at Screening is performed within 7 days of C1D1, the Screening assessment can be used and does not need to be repeated at C1D1 (predose).
EQ-5D-3L Questionnaire	X	X		X			X		X	X			Administered predose and prior to other procedures during treatment visits
Pharmacokinetic and Biomarker Assessments		X	X	X		X	X	X	X see note				For Cycles ≥ 3, obtain stool sample if subject has Grade ≥ 3 diarrhea or colitis. Request representative fragment of tissue and/or representative section of paraffin block from biopsy if taken for colitis or Grade ≥ 3 diarrhea.
	See Table 2 for detailed schedule												
Duvelisib Self-Administration Diary		X	X	X	X	X	X	X	X				First year on treatment only
Duvelisib Administration (Please see required and recommended prophylaxis in Section 6.6.1)		X (C1D14 AM dose in clinic)	X	X	X	X	X	X					Administration of the first dose should be scheduled to occur within 1 week after randomization. See Section 6.1 for dosing schedule.

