### 4.2 General Presentation Considerations

Baseline is defined as the last available pre-treatment assessment (scheduled or unscheduled). 'Treatment Day' will be calculated relative to the date of randomization, i.e., Treatment Day = Assessment Date - First Dose Date + 1.

The following visit windows will be defined for the purposes of determination of ORR per Lugano and revised IWG criteria at 6, 12, 18 and 24 months:

Timepoint	Visit Window
Month 6	155 – 211 (183 ± 28 days) from first dose
Month 12	351 - 407 days (379 ± 28 days) from first dose
Month 18	463 – 519 days (491± 28 days) from first dose
Month 24	687 – 743 days (715 ± 28 days) from first dose

For other by-visit summaries, data will be categorized based on the scheduled visit (i.e. cycle) specified on the eCRF on which the data were collected.

Continuous data will be summarized in terms of the mean, standard deviation (SD), median, minimum, maximum and number of observations, unless otherwise stated. Continuous data that are expected to be skewed will be presented in terms of the maximum, upper quartile, median, lower quartile, minimum and number of observations. The minimum and maximum will be reported to the same number of decimal places as the raw data recorded in the database. The mean, median, lower quartile and upper quartile will be reported to one more decimal place than the raw data recorded in the database. The SD will be reported to two more decimal places than the raw data recorded in the database. In general, the maximum number of decimal places reported shall be four for any summary statistic.

Categorical data will be summarized in terms of the number of subjects providing data at the relevant time point (n), frequency counts and percentages. Any planned collapsing of categories will be detailed in the SAP text and the data displays.

Percentages will be presented to one decimal place. Percentages will not be presented for zero counts. Percentages will be calculated using n as the denominator. If sample sizes are small, the data displays will show the percentages, but any textual report will describe frequencies only.

Changes from baseline in categorical data will be summarized using shift tables where appropriate.

P-values greater than or equal to 0.001, in general, will be presented to three decimal places. P-values less than 0.001 will be presented as “<0.001”.

Confidence intervals (CIs) will be presented to one more decimal place than the raw data.

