#### 4.5 Analysis Sets

##### Modified Intent-to-treat (mITT) Analysis Set

The modified intent-to-treat (mITT) analysis set will include all subjects who receive at least one dose of study drug. The mITT analysis set will serve as the primary analysis set for all efficacy endpoints and baseline characteristics.

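### PFS starts at first dose, but two censoring rows in SAP Table 1 count from randomization and so give zero or negative PFS times

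*SAP*

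**What the plan says.** **Time origin.** SAP 4.10.3 states: "PFS will be assessed using KM methods from time of first dose of study intervention to PD or death". Protocol 9.4.3 defines the same origin. For the handling of events and censoring, SAP 4.10.3 directs the reader elsewhere: "See Table 1 for event and censoring definitions".

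**Censoring date.** In SAP Table 1, two rows share the date "Date of randomization + 1 day". One covers subjects without an adequate baseline assessment. The other covers subjects without an adequate post-baseline assessment, except where death comes before the first scheduled one. The other censoring rows use the date of an actual disease assessment.

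**Gap between the two anchors.** The randomization row of the protocol's Schedule of Activities (Section 1.3) gives a window of Day -7 to Day -1. The drug administration row adds: "Administration of the first dose should be scheduled to occur within 1 week after randomization".

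**Who is analysed.** Secondary efficacy uses the mITT set, which "will include all subjects who receive at least one dose of study drug" (SAP 4.5). Every subject in the PFS analysis therefore has a first-dose date.

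**Day counting.** The SAP gives no formula for PFS duration. For Treatment Day, SAP 4.2 gives "Treatment Day = Assessment Date - First Dose Date + 1".

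**The concern.** A duration needs its start and end measured from compatible anchors. Here the clock starts at first dose, while the stop date in two rows is fixed one day after an event that the schedule places before first dose. Applied literally, the rule censors a subject before, or at best on, the day follow-up begins.

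What is at stake is the accounting, not the estimate. SAP 4.2 reports the number of events and the number censored for PFS, Protocol 9.4.1 asks for the number and percentage censored, and SAP 4.10.3 calls for a by-subject PFS listing. PFS is also produced under both sets of response criteria and by arm, so any discrepancy would appear more than once. A programmer who meets a negative time has no written instruction and must reset it, exclude it or ask.

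**Working it through.** **Inputs**

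- Origin: date of first dose (SAP 4.10.3; Protocol 9.4.3).
- Censoring date in the two rows: randomization date + 1 (SAP Table 1).
- Lag L = first dose date minus randomization date. Randomization on Day -7 to Day -1 with first dose on Day 1, and no Day 0, gives L = 1 to 7 days (Protocol 1.3). For example, randomization on Day -1 gives L = 1.
- The plan states no PFS figure that could be reproduced. This is date arithmetic only.

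**Formulas**

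- Plain difference: PFS = (randomization + 1) - first dose = 1 - L.
- With one day added: PFS = (randomization + 1) - first dose + 1 = 2 - L.

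**Results**

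| L (days) | 1 - L | 2 - L | Censoring date relative to first dose |
|---|---|---|---|
| 1 | 0 | 1 | same day |
| 2 | -1 | 0 | before |
| 3 | -2 | -1 | before |
| 4 | -3 | -2 | before |
| 5 | -4 | -3 | before |
| 6 | -5 | -4 | before |
| 7 | -6 | -5 | before |

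The censoring date falls before first dose for 6 of the 7 permitted lags, whichever formula is used. Negative durations arise for 6 of 7 lags with the plain difference and for 5 of 7 with the added day. In the second case L = 2 gives zero and L = 1 gives a valid 1 day. Same-day dosing (L = 0), which the schedule does not show, would give +1 or +2 days.

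**Effect on the Kaplan-Meier estimate.** A subject censored before the first event is in no risk set at any event time, so the product of conditional survival probabilities is the same wherever that early censoring is placed. An illustration on simulated data used 46 assessable subjects and 5 unassessable ones (both counts assumed), with no event before day 60. The unassessable subjects were censored at day -6, day 0 or day +1, or dropped. The 6-month and 12-month estimates were 0.630 and 0.435 in all four cases. Only the count changed: 51 records when they were kept and 46 when they were dropped.

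**After the change.** Censoring at first dose gives (first dose - first dose) + 1 = 1 day for every such subject, whatever the lag. Without the added day the same cell text would give 0, so the formula has to be stated along with the date.

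**The case against.** The strongest reply is that nothing inferential depends on this. PFS is secondary, Protocol 9.4.1 limits hypothesis testing to ORR, and no formal comparison of arms is planned. The estimates do not move. The two rows may also be nearly empty: inclusion criterion 4 requires a measurable lesion, and an end-of-treatment scan is required if none was done in the previous 30 days. Affected subjects would still be visible elsewhere, because the primary ORR keeps the full mITT denominator and counts subjects without a response as non-responders (SAP 4.10.2). SAP 4.1 provides for independent checking of all outputs, and the revision history shows that a dry run had already prompted changes. All of this stands, and it makes the point minor.

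Three stronger readings are tempting, and the documents do not support them:

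- *Most affected subjects will have negative times.* Six of seven counts permitted days, not subjects. No lag distribution is given, so the share censored before first dose could be anywhere from none (all randomized on Day -1) to all (all on Day -7 to Day -2).
- *The PFS table will silently lose subjects.* The SAP nowhere says that non-positive times are deleted. Exclusion is one possible outcome, and the listing or the checking could bring the problem to light.
- *The PFS N will fall by a particular number from the planned 51 per arm.* Nothing in the documents gives the number of subjects without an adequate assessment.

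The reply does not remove the contradiction. Checking outputs against a specification cannot settle what the specification should have said, and no passage sets a floor or corrects the date.

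**Conclusion.** The rule is wrong as written, with a small consequence. For subjects in the two rows, the stated origin and the stated censoring date give a PFS time of 0 to -6 days, or +1 to -5 days with the added day. This rests on the protocol's Day -7 to Day -1 window being kept. The first-dose timing is worded as a scheduling target, so a longer delay would make the value more negative still.

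Kaplan-Meier percentiles and the 6- and 12-month estimates are unaffected, provided that no PFS event occurs by Day 1. What can go wrong is the PFS listing, which would show impossible durations, and the reported N and number censored, if non-positive times are excluded. The number of subjects concerned is unknown and could be zero.

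The mismatch looks like an anchor left over from a randomization-based definition. SAP 4.2 has a similar slip: its text describes Treatment Day as relative to randomization, while its formula uses first dose. That is an inference about origin, and the conclusion does not depend on it.

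**What to change.** 1. In both rows of SAP Table 1, replace the randomization-based date with the date of first dose (Day 1).
2. In SAP 4.10.3, add one sentence: PFS in days equals the date of event or censoring, minus the date of first dose, plus 1. This matches the day counts already used for Treatment Day (SAP 4.2), exposure duration (SAP 4.11.1) and time to onset of adverse events (SAP 4.11.2.1).

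Subjects in these rows are then censored at 1 day and remain in the mITT N and in the number censored.

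The cost is two table cells and one sentence, with no new data. If the programs now use a plain date difference, every PFS time lengthens by one day, which has no practical effect. The Treatment Day sentence in SAP 4.2 can be aligned with its formula in the same revision.
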